1.1.11 Rationale for permitting continued treatment in select cases of PD

Immune therapies have been noted to be associated with atypical responses known as tumor flare or immune related response.^{79,80} There is increasing evidence that subjects treated with immune therapies including checkpoint inhibitors may manifest disease progression (by conventional response criteria) before demonstrating clinical objective responses and/or stable disease. Ongoing clinical trials with nivolumab have reported this phenomenon in approximately 10% of subjects.⁸¹ Similar response has also been observed with other immune therapies. Treatment with antiviral agent in combination with interleukin-12 demonstrated evidence of objective responses after an

initial Progressive Disease (PD) in a patient with human immunodeficiency virus related kaposi sarcoma.⁸² The exact etiology for this phenomenon remains unknown. There is suggestion that enhanced inflammation within tumors results in increase in tumor size which may manifest as enlarged index lesions and as newly visible small non-index lesions. Over time, both the malignant and inflammatory portions of the mass may then decrease leading to overt signs of clinical improvement. Alternatively, in some individuals, the kinetics of tumor growth may initially outpace anti-tumor immune activity. With sufficient time, the anti tumor activity will dominate and become clinically apparent. Given the observation of this phenomenon, subjects will be allowed to continue study therapy (nivolumab and brentuximab vedotin) after initial investigator-assessed Response Evaluation Criteria (Lugano Lymphoma 2014, Response Criteria in MF/SS; consensus Global Response Score) defined progression.^{83,84} If the subjects are assessed to be deriving clinical benefit and if they continue to meet the following criteria;

1. Investigator-assessed clinical benefit
2. Stable performance status
3. Treatment beyond disease progression will not delay an imminent intervention to prevent serious complications of disease progression
4. Subject will be re-consented for treatment beyond progressive disease
5. Tolerance of study drug

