Progressive disease Individual target nodes/nodal masses Extranodal lesions	Progressive metabolic disease Score 4 or 5 with an increase in intensity of uptake from baseline and/or New FDG-avid foci consistent with lymphoma at interim or end-of-treatment assessment	Progressive disease requires at least 1 of the following PPD progression: An individual node/lesion must be abnormal with: LDi > 1.5 cm and Increase by ≥ 50% from PPD nadir and An increase in LDi or SDi from nadir 0.5 cm for lesions ≤ 2 cm 1.0 cm for lesions > 2 cm In the setting of splenomegaly, the splenic length must increase by > 50% of the extent of its prior increase beyond baseline (eg, a 15-cm spleen must increase to > 16 cm). If no prior splenomegaly, must increase by at least 2 cm from baseline New or recurrent splenomegaly
Nonmeasured lesions	None	New or clear progression of preexisting nonmeasured lesions

(continued on following page)

Response and Site	PET-CT-Based Response	CT-Based Response
New lesions	New FDG-avid foci consistent with lymphoma rather than another etiology (eg, infection, inflammation). If uncertain regarding etiology of new lesions, biopsy or interval scan may be considered	Regrowth of previously resolved lesions A new node > 1.5 cm in any axis A new extranodal site > 1.0 cm in any axis; if < 1.0 cm in any axis, its presence must be unequivocal and must be attributable to lymphoma Assessable disease of any size unequivocally attributable to lymphoma
Bone marrow	New or recurrent FDG-avid foci	New or recurrent involvement

Abbreviations: 5PS, 5-point scale; CT, computed tomography; FDG, fluorodeoxyglucose; IHC, immunohistochemistry; LDi, longest transverse diameter of a lesion; MRI, magnetic resonance imaging; PET, positron emission tomography; PPD, cross product of the LDi and perpendicular diameter; SDi, shortest axis perpendicular to the LDi; SPD, sum of the product of the perpendicular diameters for multiple lesions.

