 - b) CT based response: Target node/nodal masses must regress to ≤ 1.5 cm in LDi, with no extralymphatic sites of disease.

Organ involvement: Absence of organomegaly (Table 3).

- 2) Bone marrow: No evidence of FDG-avid disease in marrow. If there was evidence of involvement of bone marrow with lymphoma at screening/baseline and a biopsy was performed (PTCL), a bone marrow biopsy will be required to confirm CR.
- 3) The presence of residual symptoms in the absence of detectable disease by imaging does not preclude the designation of CR.

PR (Partial Remission)

The designation of PR requires all of the following:

- 1) PET-CT based response: Score of 4 or 5, provided reduced uptake compared with base line and absence of structural progression development on CT Scan.

- 2) CT based response: $\geq 50\%$ regression in SPD of upto 6 measurable nodal and extranodal lesions (Table 3) .
- 3) Splenic and hepatic nodules must regress by $\geq 50\%$ in length beyond normal.

Bone marrow : reduced uptake compared with baseline. If there is evidence of nodal response but persistent focal changes in the marrow consider further evaluation (Table 3).

SD (Stable Disease)

SD is defined as the following:

- 1) PET-CT based response: no metabolic response, score of 4 or 5 with no significant changes from baseline.
- 2) CT based response: $< 50\%$ decrease from baseline, absence of new lesions (Table 3).
- 3) Bone marrow: no change from baseline.

PD: Relapsed Disease (after CR)/Progressive Disease (after PR, SD)

- 1) PET-CT based response: Score of 4 or 5 with increase in intensity from baseline or interim scan/ or any new FDG avid focus consistent with malignant lymphoma (Table 3).
- 2) CT based response: New node, new or recurrent splenomegaly, progression of existing lesions (Table 3).

IR (INDETERMINATE RESPONSE)

A patient will be considered to have Indeterminate Response (IR) in one or more of the 3 following circumstances

- 1) Increase in overall tumor burden (as assessed by SPD) of $\geq 50\%$ of up to 6 measurable lesions in the first 12 weeks of therapy, without clinical deterioration (IR(1))
- 2) Appearance of new lesions; or growth of one or more existing lesion(s) of $\geq 50\%$ at any time point during treatment occurring in the context of lack of overall progression ($<50\%$ increase) of overall tumor burden, as measured by SPD of up to 6 lesions at any time during the treatment (IR(2))

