- 3) Increase in FDG uptake of one or more lesion(s) without a concomitant increase in lesion size or number (IR(3))

It is possible that, at a single time point a subject could fulfill criteria for both IR(1 or 2) AND IR(3): for example, there could be a new FDG-avid lesion in the absence of overall progression (IR(2)), and, at the same time, increase in FDG uptake of a separate lesion (IR(3)). In such cases, the designation of IR(1 or 2) should take priority (eg, IR(2))

Follow-up of IR

- 1) In patients categorized as having any of the above types of IR, it is mandatory to obtain a repeat imaging after an additional 12 weeks (or earlier if clinically indicated). At that time, response should be re-evaluated and the patient should be considered to have true PD if the SPD of target lesion has increased further, with the considerations below:
- 2) In the case of IR(1), the comparison should be between the first IR(1) and the current SPD, with an increase of >10% constituting PD. In addition there should be an increase of > 5 mm (in either dimension) of at least one lesion for lesions < 2 cm, and 10 mm for lesions > 2 cm, to be consistent with the Lugano classification (3)(Table 2). The 10% threshold is empiric but designed to account for variability in measurement (37), especially when taken along with the minimum increase. If the target SPD increase is < 10%, the response would still be categorized as IR(1), and the patient could continue treatment until a subsequent scan shows either true PD (> 10% increase from first IR(1) time point and an increase of > 5mm in either dimension of at least one lesion) or response (>50% decrease from baseline). In this situation, it is reasonable to repeat imaging in 4-8 weeks of the original IR(1) timepoint to ensure absence of significant further increase.
- 3) In the case of IR(2), the new or growing lesion(s) (unless biopsy proven to be benign) should be added to the target lesion(s), up to a total of no more than 6 total lesions. If the SPD of the newly defined set of target lesions has increased > 50% from the nadir value which may precede the IR time point. The patients is considered to have PD.
- 4) In the case of IR(3), since inflammatory responses may result in an increase in the standardized uptake value of a lesion, the patient will not be considered to have PD unless there is evidence of PD by an increase in lesion size or the development of new lesions, as noted above

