- 5) Importantly, if a patient is assessed as having IR and then “true” PD at a subsequent time point (without an intervening objective response between IR and PD), the IR assessment should subsequently be corrected to PD for reporting purposes to the date of the prior designation of IR

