4.2 Secondary Endpoints

The secondary endpoints are DOR, CR rate, duration of CR, PFS and OS. All these endpoints are based on Lugano classification 2014 and Global Response score for the CTCL subjects.

DOR will be calculated from the date of initial documentation of a response (CR, or PR) to the date of first documented evidence of progressive disease (or relapse for subjects who experience CR during the study) or death due to any cause, whichever occurs first. Subjects who are progression-free and alive or have unknown status will be censored at the last tumor assessment. For subjects who received subsequent therapy prior to documented progression, duration of response will be censored on the last tumor assessment date prior to or on subsequent therapy. Allogeneic SCT and ASCT will be considered as subsequent therapy.

The CR rate is defined as the number of subjects with a BOR of CR divided by the number of treated subjects. The duration of CR will only be evaluated in subjects with BOR of CR and is defined as the time from first documentation of CR to the date of relapse or death due to any cause, whichever occurs first. Censoring will be applied as per DOR definition.

PFS is defined as the time from the date of first dose of study drug until the date of first documented evidence of progressive disease (or relapse for subjects who experience CR during the study) or death due to any cause, whichever comes first. Subjects who are progression-free and alive or have unknown status will be censored at the last tumor assessment. Subjects who did not have any on-study tumor assessments and did not die will be censored on the date of first treatment. For subjects who received subsequent therapy prior to documented progression, it will be censored on the last tumor assessment date prior to or on subsequent therapy.

Situation	Date of Progression or Censoring	Outcome
No baseline tumor assessments	First dose date	Censored
No on study tumor assessments and no death	First dose date	Censored
New anticancer treatment started without a prior reported progression or death	Date of last evaluable tumor assessment prior to or on the date of initiation of the subsequent anti-cancer therapy	Censored
Progression documented at scheduled or unscheduled visit and no new anticancer treatment started before	Date of the first documented tumor progression	Progressed
Subject progression free and no new anticancer treatment started	Date of last tumor assessment	Censored

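### Appendix 2 can label one scan both Lugano progression and indeterminate response, and the Lugano-only endpoint rules in the SAP do not reconcile the two

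*Protocol*

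**What the plan says.** Appendix 2 sets the response rules for DLBCL, PTCL, PMBL and MGZL. For PET, Table 1 counts as progression "New FDG-avid foci consistent with lymphoma at interim or end-of-treatment assessment", and the PD text below it reads "Score of 4 or 5 with increase in intensity from baseline or interim scan/ or any new FDG avid focus consistent with malignant lymphoma". The CT line of that text reads "CT based response: New node, new or recurrent splenomegaly, progression of existing lesions", with size thresholds in Table 1.

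The same appendix then defines IR. IR(2) is "Appearance of new lesions; or growth of one or more existing lesion(s) of" at least 50%, while the SPD of up to six lesions rises by less than 50%. IR(3) is rising FDG uptake with no increase in lesion size or number. Imaging must be repeated 12 weeks later, or sooner if clinically indicated. If true PD then follows with no objective response in between, item 5 of the follow-up rules says "the IR assessment should subsequently be corrected to PD for reporting purposes to the date of the prior designation of" IR. Appendix 4 repeats the IR text for CTCL.

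For the endpoints, Protocol 8.3.1 and SAP 4.1 assess ORR by Lugano (Global Response Score for CTCL). The best-overall-response (BOR) window closes at first documented progression or subsequent therapy. SAP 4.2 says of the secondary endpoints: "All these endpoints are based on Lugano classification 2014 and Global Response score for the CTCL subjects". SAP Table 4.2-1 has no row for IR, and Protocol 1.3.3 and 8.3.3 make IR exploratory. Yet Protocol 5.4 defines objective response by Lugano and LYRIC together, and Protocol 4.5.9.1 cites both for progression.

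**The concern.** The PD and IR definitions overlap. Item 5 speaks of correcting an IR to PD, which implies that IR stands in place of PD until then. SAP 4.2 implies the opposite for the endpoints: under Lugano, a scan that meets the PD criteria is an event when it is taken. A site that follows Appendix 2 literally and an analyst who follows the SAP literally can therefore reach different outcomes for the same subject.

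At stake are PFS, DOR and duration of CR, and also the primary ORR, because a documented progression closes the BOR window. A response that appears after the scan counts if the scan was labelled IR and does not count if it was labelled PD.

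**Working it through.** **1. Does one scan meet both definitions?** Inputs: the PD and IR criteria in Appendix 2. The lesion sizes are constructed examples.

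- *Growth of one lesion.* Six lesions of 20 × 20 mm, one growing to 30 × 30 mm. Its product goes from 400 to 900 mm², (900 − 400)/400 = +125%, and its long diameter gains 10 mm, so it is Lugano PD on CT. SPD goes from 6 × 400 = 2400 to 2900 mm², 500/2400 = +20.8%, so it is also IR(2).
- *New node in a responder.* Five lesions of 30 × 30 mm (SPD 4500) shrink to 18 × 18 mm (SPD 1620, −64%), then a new 20 × 20 mm node appears. A new node over 1.5 cm is Lugano PD. SPD is now 1620 + 400 = 2020, +24.7% from nadir, so it is also IR(2). It becomes true PD under the IR(2) follow-up rule only above +50% from nadir.
- *Uptake only.* A score of 4 or 5 with increased intensity is PD. With no growth and no new lesion it is also IR(3), which the follow-up text says is not PD unless size or number increases.

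**2. Is there a ranking?** The one priority sentence puts IR(1) or IR(2) ahead of IR(3). It does not rank any IR against PD. Appendix 2's own illustration of IR(2) is a new FDG-avid lesion, which its PD text also covers when the lesion is consistent with lymphoma.

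**3. When does the label matter?** Take a responder at week 6 with such a scan at week 12. SAP section 8 gives months = (last − first + 1)/30.4375. An event at week 12 gives PFS (84 + 1)/30.4375 = 2.79 months and DOR (42 + 1)/30.4375 = 1.41 months.

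| Course after week 12 | Lugano PD recorded | Only IR recorded |
|---|---|---|
| True PD at week 24, no response between | Event, PFS 2.79, DOR 1.41 | Same: item 5 back-dates to week 12 |
| Never confirmed, last scan week 48 | Event, PFS 2.79, DOR 1.41 | Censored, PFS 337/30.4375 = 11.07, DOR 295/30.4375 = 9.69 |
| New therapy, no repeat scan | Event, PFS 2.79 | Censored at the same scan (Table 4.2-1) |
| Death, no repeat scan | Event at week 12 | Event at date of death |
| Response, then PD at week 39 | Event, PFS 2.79, DOR 1.41 | Event, PFS 274/30.4375 = 9.00, DOR 232/30.4375 = 7.62 |

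A missing repeat scan is possible although Appendix 2 makes it mandatory: Protocol 4.5.9.4 requires no further imaging once post-progression treatment stops, apart from the transplant follow-up.

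**4. Scale for the primary endpoint, for illustration.** The plan's own interval reproduces: 24/40 responders gives a two-sided 80% Clopper-Pearson interval of 48.6% to 70.6%. Protocol 1.1.11, on progression before response or stable disease, says: "Ongoing clinical trials with nivolumab have reported this phenomenon in approximately 10% of subjects". In B1 that is 0.10 × 40 = 4 subjects. Suppose all four had no response before the dual-label scan and responded after it. The count is then 24 under IR and 20 under Lugano. 20/40 gives 38.8% to 61.2%, which no longer excludes the 40% null. This is an upper bound under favourable assumptions, not an estimate.

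**The case against.** The strongest reply is that the governing criterion is already stated. SAP 4.2 names Lugano, Protocol 8.3.1 and 5.4.5 agree, and IR is exploratory. Protocol 4.5.9.1 and 4.5.9.2 can also be read so that LYRIC monitoring starts only after progression has been recorded, in which case PD is in the data. This is a fair reading and it stands as one of two. Item 5 and the IR(3) follow-up text support the other, and Protocol 5.4 applies both criteria to objective response. The conflict is unreconciled rather than a complete absence of a rule.

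Three stronger inferences are tempting, and the documents do not support them.

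- *IR replaces PD in the database, so PFS and DOR are biased upward.* This depends on the case report form and its completion guidelines, which are not among the documents. Lesion measurements are entered in the eCRF, so CT-based PD may be derivable. The public SAP also has gaps where exploratory IR analyses may have stood, though the visible Table 4.2-1 has no IR row.
- *The event and its date always depend on the label.* Item 5 makes both match Lugano when PD is confirmed with no response in between.
- *Every IR is a Lugano PD.* IR(2) and IR(3) lack Lugano's size, score and aetiology conditions. An extranodal lesion growing from 12 × 10 to 15 × 13 mm goes from 120 to 195 mm², +62.5%, and can be IR(2). Its long diameter gains 3 mm and does not exceed 1.5 cm, so it is not CT progression. Rising uptake at score 3 or below can be IR(3) but is not PET progression.

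**Conclusion.** The point holds as an unreconciled conflict in Appendix 2, repeated for CTCL in Appendix 4, that the SAP does not settle. It affects results in only four situations: IR never confirmed, IR followed by new therapy without repeat imaging, IR followed by death without repeat imaging (date only), and IR followed by a response. There PFS and DOR depend on the label recorded. So does ORR, when the response comes only after the scan.

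If only IR is recorded, the direction is upward. The documents do not give the size. They state neither how many first progressions would also meet IR nor how those subjects would then fare, so any figure for the shift in PFS would rest on assumed inputs. The figure of about 4 of 40 DLBCL subjects comes from a general nivolumab rate that is not specific to lymphoma, this combination or LYRIC. The plan should be clarified before analysis, because an exploratory classification should not alter the primary and secondary endpoints.

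**What to change.** State in Appendix 2 (with the matching CTCL text in Appendix 4), Protocol 5.4 and SAP 4.1 and 4.2:

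- At each assessment the investigator records the Lugano 2014 response (Global Response Score for CTCL) and, separately, any LYRIC IR category.
- BOR and ORR, PFS, DOR and duration of CR use the first Lugano (or Global Response Score) PD, regardless of IR.
- LYRIC-based versions of these endpoints are exploratory or sensitivity analyses.

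Add an IR row to SAP Table 4.2-1. For data already recorded as IR only, do not convert every IR to PD, which would create false events. Apply the Lugano PD criteria to the recorded measurements and PET scores, and query the site where these are insufficient. Treatment decisions after an IR are untouched.

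The cost is a second response field or a derivation rule, a clarification to sites, and a few sentences in the two documents. Reported PFS, DOR and ORR may be slightly less favourable.

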APPENDIX 3 CUTANEOUS T CELL LYMPHOMA ISCL/EORTC STAGING CRITERIA

Table 2: Modified ISCL/EORTC Revisions to the TNMB Classification of MF/SS

TNMB Stages	Description of TNMB
Skin*	
T ₁	Limited patches, papules, and/or plaques covering < 10% of the skin surface; may further stratify into T _{1a} (patch only) v T _{1b} (plaque ± patch)
T ₂	Patches, papules, or plaques covering ≥ 10% of the skin surface; may further stratify into T _{2a} (patch only) v T _{2b} (plaque ± patch)
T ₃	One or more tumors (≥ 1 cm diameter)
T ₄	Confluence of erythema covering ≥ 80% body surface area
Node†	
N ₀	No clinically abnormal lymph nodes; biopsy not required
N ₁	Clinically abnormal lymph nodes; histopathology Dutch grade 1 or NCI LN ₀₋₂
N _{1a}	Clone negative
N _{1b}	Clone positive
N ₂	Clinically abnormal lymph nodes; histopathology Dutch Grade 2 or NCI LN ₃
N _{2a}	Clone negative
N _{2b}	Clone positive
N ₃	Clinically abnormal lymph nodes; histopathology Dutch grade 3-4 or NCI LN ₄ ; clone positive or negative
N _x	Clinically abnormal lymph nodes without histologic confirmation or inability to fully characterize the histologic subcategories
Visceral	
M ₀	No visceral organ involvement
M ₁	Visceral involvement (must have pathology confirmation and organ involved should be specified)
Blood	
B ₀	Absence of significant blood involvement: ≤ 5% of peripheral blood lymphocytes are atypical (Sézary) cells
B _{0a}	Clone negative
B _{0b}	Clone positive
B ₁	Low blood tumor burden: > 5% of peripheral blood lymphocytes are atypical (Sézary) cells but does not meet the criteria of B ₂
B _{1a}	Clone negative
B _{1b}	Clone positive
B ₂	High blood tumor burden: ≥ 1,000/μL Sézary cells with positive clone‡; one of the following can be substituted for Sézary cells: CD4/CD8 ≥ 10, CD4+CD7- cells ≥ 40% or CD4+CD26- cells ≥ 30%

Abbreviations: ISCL, International Society for Cutaneous Lymphomas; EORTC, European Organisation for Research and Treatment of Cancer; MF, mycosis fungoides; SS, Sézary syndrome; NCI, National Cancer Institute.
 *Patch = any size lesion without induration or significant elevation above the surrounding uninvolved skin; poikiloderma may be present. Plaque = any size lesion that is elevated or indurated; crusting or poikiloderma may be present. Tumor = any solid or nodular lesion ≥ 1 cm in diameter with evidence of deep infiltration in the skin and/or vertical growth.
 †Lymph node classification has been modified from 2007 ISCL/EORTC consensus revisions¹ to include central nodes. Lymph nodes are qualified as abnormal if > 1.5 cm in diameter.
 ‡The clone in the blood should match that of the skin. The relevance of an isolated clone in the blood or a clone in the blood that does not match the clone in the skin remains to be determined.

**APPENDIX 4 MODIFIED SEVERITY WEIGHTED ASSESSMENT TOOL /
GLOBAL RESPONSE SCORE**

Table 3: Modified Severity Weighted Assessment Tool

Body Region	% BSA in Body Region	Assessment of Involvement in Patient's Skin		
		Patch*	Plaque†	Tumor‡
Head	7			
Neck	2			
Anterior trunk	13			
Arms	8			
Forearms	6			
Hands	5			
Posterior trunk	13			
Buttocks	5			
Thighs	19			
Legs	14			
Feet	7			
Groin	1			
Subtotal of lesion BSA				
Weighting factor		×1	×2	×4
Subtotal lesion BSA × weighting factor				

NOTE. mSWAT score equals summation of each column line.
Abbreviations: BSA, body surface area; mSWAT, modified Severity Weighted Assessment Tool.
*Any size lesion without induration or significant elevation above the surrounding uninvolved skin; poikiloderma may be present.
†Any size lesion that is elevated or indurated; crusting, ulceration, or poikiloderma may be present.
‡Any solid or nodular lesion ≥ 1 cm in diameter with evidence of deep infiltration in the skin and/or vertical growth.

Table 4: Response in Skin

Response	Definition
Complete response	100% clearance of skin lesions*
Partial response	50%-99% clearance of skin disease from baseline without new tumors (T ₃) in patients with T ₁ , T ₂ or T ₄ only skin disease
Stable disease	< 25% increase to < 50% clearance in skin disease from baseline without new tumors (T ₃) in patients with T ₁ , T ₂ , or T ₄ only skin disease
Progressive disease†	
≥ 25% increase in skin disease from baseline or
 
New tumors (T₃) in patients with T₁, T₂ or T₄ only skin disease or
 
Loss of response: in those with complete or partial response, increase of skin score of greater than the sum of nadir plus 50% baseline score

Relapse	Any disease recurrence in those with complete response

NOTE. Based on modified Severity Weighted Assessment Tool score.

*A biopsy of normal appearing skin is unnecessary to assign a complete response. However, a skin biopsy should be performed of a representative area of the skin if there is any question of residual disease (persistent erythema or pigmentary change) where otherwise a complete response would exist. If histologic features are suspicious or suggestive of mycosis fungoides/Sézary syndrome (see histologic criteria for early mycosis fungoides⁷), the response should be considered a partial response only.

†Whichever criterion occurs first.

Table 5: Response in Lymph Nodes*

Response	Definition
CR	All lymph nodes are now ≤ 1.5 cm in greatest transverse (long axis) diameter by method used to assess lymph nodes at baseline or biopsy negative for lymphoma; in addition, lymph nodes that were N ₃ classification and ≤ 1.5 cm in their long axis and > 1 cm in their short axis at baseline, must now be ≤ 1 cm in their short axis or biopsy negative for lymphoma
PR	Cumulative reduction $\geq 50\%$ of the SPD of each abnormal lymph node at baseline and no new lymph node > 1.5 cm in the diameter of the long axis or > 1.0 cm in the diameter of the short axis if the long axis is 1-1.5 cm diameter
SD	Fails to attain the criteria for CR, PR, and PD
PD†	$\geq 50\%$ increase in SPD from baseline of lymph nodes or Any new node > 1.5 cm in the long axis or > 1 cm in the short axis if 1-1.5 cm in the long axis that is proven to be N ₃ histologically or Loss of response: $> 50\%$ increase from nadir in SPD of lymph nodes in those with PR
Relapse	Any new lymph node > 1.5 cm in the long axis in those with CR proven to be N ₃ histologically

Abbreviations: CR, complete response; PR, partial response; SPD, sum of the maximum linear dimension (major axis) \times longest perpendicular dimension (minor axis); SD, stable disease; PD, progressive disease.
*Peripheral and central lymph nodes.
†Whichever criterion occurs first.

Table 6: Response in Viscera

Response	Definition
CR	Liver or spleen or any organ considered involved at baseline should not be enlarged on physical exam and should be considered normal by imaging; no nodules should be present on imaging of liver or spleen; any post treatment mass must be determined by biopsy to be negative for lymphoma
PR	≥ 50% regression in any splenic or liver nodules, or in measurable disease (SPD) in any organs abnormal at baseline; no increase in size of liver or spleen and no new sites of involvement
SD	Fails to attain the criteria for CR, PR, or PD
PD*	> 50% increase in size (SPD) of any organs involved at baseline or New organ involvement or Loss of response: > 50% increase from nadir in the size (SPD) of any previous organ involvement in those with PR
Relapse	New organ involvement in those with CR

Abbreviations: CR, complete response; PR, partial response; SPD, sum of the maximum linear dimension (major axis) × longest perpendicular dimension (minor axis); SD, stable disease; PD, progressive disease.
*Whichever criterion occurs first.

Table 7: Response in Blood*

Response	Definition
CR†	B_0
PR‡	> 50% decrease in quantitative measurements of blood tumor burden from baseline in those with high tumor burden at baseline (B_2)
SD	Fails to attain criteria for CR, PR, or PD
PD§	B_0 to B_2 or > 50% increase from baseline and at least 5,000 neoplastic cells/ μ L ³⁶ or Loss of response: in those with PR who were originally B_2 at baseline, > 50% increase from nadir and at least 5,000 neoplastic cells/ μ L
Relapse	Increase of neoplastic blood lymphocytes to $\geq B_1$ in those with CR

Abbreviations: CR, complete response; PR, partial response; SD, stable disease; PD, progressive disease.

*As determined by absolute numbers of neoplastic cells/ μ L.

†If a bone marrow biopsy was performed at baseline and determined to unequivocally be indicative of lymphomatous involvement, then to confirm a global CR where blood assessment now meets criteria for B_0 , a repeat bone marrow biopsy must show no residual disease or the response should be considered a PR only.

‡There is no PR in those with B_1 disease at baseline as the difference within the range of neoplastic cells that define B_1 is not considered significant and should not affect determination of global objective response.

§Whichever occurs first.

Table 8: Global Response Score

Global Score*	Definition	Skin	Nodes	Blood	Viscera
CR	Complete disappearance of all clinical evidence of disease	CR	All categories have CR/NI		
PR	Regression of measurable disease	CR	All categories do not have a CR/NI and no category has a PD		
		PR	No category has a PD and if any category involved at baseline, at least one has a CR or PR		
SD	Failure to attain CR, PR, or PD representative of all disease	PR	No category has a PD and if any category involved at baseline, no CR or PR in any		
		SD	CR/NI, PR, SD in any category and no category has a PD		
PD	Progressive disease		PD in any category		
Relapse	Recurrence disease in prior CR		Relapse in any category		

Abbreviations: CR, complete response; NI, noninvolved; PR, partial response; PD, progressive disease; SD, stable disease.
*It is recommended that not only the proportion of patients who achieve a response or an unfavorable outcome be calculated but a life table account for the length of the interval during which each patient is under observation also be generated.

Response Evaluation in CTCL:

Response in CTCL will be evaluated based on the involvement of different sites (lymph nodes, viscera, skin and blood) using the TNMB staging (as clinically indicated) and will be incorporated in the Global Response Score. The m SWAT will be used for skin scoring.

All responses to be designated as CR or PR, should be documented for at least 4 weeks in duration. No CR can be ascribed to a study drug while a patient remains on concomitant therapy (such as topical steroids) with known efficacy in MF/SS.

In certain cases to document CR a biopsy may be required if there are limitations on Spiral CT scan or MRI examination for lymph node or viscera evaluation and if it is deemed necessary.

Blood evaluation for Sezary syndrome: The absolute number of CD4+ CD26- determined on flow cytometry will be used to assess blood involvement. A normal value for CD+ CD26- or CD4+CD7- cells by flow cytometry is lower than 15%.

Response in skin:

m SWAT for skin scoring/evaluation, to track skin tumor burden.

CR: 100% clearance of skin lesions.

PR: 50%-99% clearance of skin disease from baseline without new tumors (T3) in patients with T1, T2 or T4 only skin disease. ($\geq 50\%$ reduction in the mSWAT score compared with baseline).

Stable disease: $< 25\%$ increase to $< 50\%$ clearance in skin disease from baseline without new tumors (T3) in patients with T1, T2, or T4 only skin disease. (Less than 50% reduction to less than 25% increase in the mSWAT score compared with baseline).

Progressive disease: $> 25\%$ increase in skin disease from baseline or new tumors (T3) in patients with T1, T2 or T4 only skin disease or Loss of response: in those with complete or partial response, increase of skin score of greater than the sum of nadir plus 50% baseline score. Relapse is any disease recurrence in those with complete response. ($\geq 25\%$ increase in the mSWAT score from baseline).

Response in the lymph nodes will be assessed using a Spiral CT Scan or MRI.

CR: all lymph nodes ≤ 1.5 cm in greatest transverse (long axis) diameter by method used to assess lymph nodes at baseline or biopsy negative for lymphoma; in addition, lymph nodes that were N3 classification and ≤ 1.5 cm in their long axis and > 1 cm in their short axis at baseline, must be ≤ 1 cm in their short axis or biopsy negative for lymphoma.

PR: cumulative reduction $\geq 50\%$ of the SPD of each abnormal lymph node at baseline and no new lymphnode > 1.5 cm in the diameter of the long axis or > 1.0 cm in the diameter of the short axis if the long axis is 1-1.5 cm diameter.

SD: fails to attain the criteria for CR, PR, and PD.

PD: > 50% increase in SPD from baseline of lymph nodes or any new node > 1.5 cm in the long axis or > 1 cm in the short axis if 1-1.5 cm in the long axis that is proven to be N3 histologically or loss of response: > 50% increase from nadir in SPD of lymph nodes in those with PR.

Relapse is any new lymph node > 1.5 cm in the long axis in those with CR proven to be N3 histologically.

Response in the viscera will be assessed using a Spiral CT Scan or MRI:

CR: (viscera): liver, spleen or any organ considered involved at baseline should not be enlarged on physical exam and should be considered normal by imaging; no nodules should be present on imaging of liver or spleen; any post treatment mass must be determined by biopsy to be negative for lymphoma.

PR: \geq 50% regression in any splenic or liver nodules, or in measureable disease (SPD) in any organs abnormal at baseline; no increase in size of liver or spleen and no new sites of involvement.

SD: Fails to attain the criteria for CR, PR, or PD.

PD: > 50% increase in size (SPD) of any organs involved at baseline or new organ involvement or loss of response: > 50% increase from nadir in the size (SPD) of any previous organ involvement in those with PR.

Relapse new organ involvement in those with CR.

Response in blood will be performed with peripheral blood flow cytometry.

CR: B0 (absence of blood involvement).

PR: > 50% decrease in quantitative measurements of blood tumor burden from baseline in those with high tumor burden at baseline (B2).

SD: Fails to attain criteria for CR, PR, or PD.

PD: B0 to B2 or > 50% increase from baseline and at least 5,000 neoplastic cells/ μ L³⁶ or loss of response: in those with PR who were originally B2 at baseline, > 50% increase from nadir and at least 5,000 neoplastic cells/ μ L.

Relapse Increase of neoplastic blood lymphocytes to \geq B1 in those with CR.

* SPD: sum of the maximum linear dimension major axis x longest perpendicular dimension minor axis.

*B1: Low tumor burden (> 5%, B1a=clone negative, B1b= clone positive).

B2: High tumor burden \geq 1000/ μ L Sezary cells with positive clone.

IR (INDETERMINATE RESPONSE)*

A patient will be considered to have Indeterminate Response (IR) in one or more of the 3 following circumstances

- 1) Increase in overall tumor burden (as assessed by SPD) of $\geq 50\%$ of up to 6 measurable lesions in the first 12 weeks of therapy, without clinical deterioration (IR(1))
- 2) Appearance of new lesions; or growth of one or more existing lesion(s) of $\geq 50\%$ at any time point during treatment occurring in the context of lack of overall progression ($<50\%$ increase) of overall tumor burden, as measured by SPD of up to 6 lesions at any time during the treatment (IR(2))
- 3) Increase in FDG uptake of one or more lesion(s) without a concomitant increase in lesion size or number (IR(3))

It is possible that, at a single time point a subject could fulfill criteria for both IR(1 or 2) AND IR(3): for example, there could be a new FDG-avid lesion in the absence of overall progression (IR(2)), and, at the same time, increase in FDG uptake of a separate lesion (IR(3)). In such cases, the designation of IR(1 or 2) should take priority (eg, IR(2))

Follow-up of IR

- 1) In patients categorized as having any of the above types of IR, it is mandatory to obtain a repeat imaging after an additional 12 weeks (or earlier if clinically indicated). At that time, response should be re-evaluated and the patient should be considered to have true PD if the SPD of target lesion has increased further, with the considerations below:
- 2) In the case of IR(1), the comparison should be between the first IR(1) and the current SPD, with an increase of $>10\%$ constituting PD. In addition there should be an increase of > 5 mm (in either dimension) of at least one lesion for lesions < 2 cm, and 10 mm for lesions > 2 cm, to be consistent with the Lugano classification (3)(Table 2). The 10% threshold is empiric but designed to account for variability in measurement (37), especially when taken along with the minimum increase. If the target SPD increase is $< 10\%$, the response would still be categorized as IR(1), and the patient could continue treatment until a subsequent scan shows either true PD ($> 10\%$ increase from first IR(1) time point and an increase of > 5 mm in either dimension of at least one lesion) or response ($>50\%$ decrease from baseline). In this situation, it is reasonable to repeat imaging in 4-8 weeks of the original IR(1) timepoint to ensure absence of significant further increase.
- 3) In the case of IR(2), the new or growing lesion(s) (unless biopsy proven to be benign) should be added to the target lesion(s), up to a total of no more than 6 total lesions. If the SPD of the newly defined set of target lesions has increased $> 50\%$ from the nadir value which may precede the IR time point. The patients is considered to have PD.
- 4) In the case of IR(3), since inflammatory responses may result in an increase in the standardized uptake value of a lesion, the patient will not be considered to have PD unless there is evidence of PD by an increase in lesion size or the development of new lesions, as noted above
- 5) Importantly, if a patient is assessed as having IR and then “true” PD at a subsequent time point (without an intervening objective response between IR and PD), the IR assessment should

subsequently be corrected to PD for reporting purposes to the date of the prior designation of IR

*Lymphoma Response to Immunomodulatory therapy Criteria (LYRIC) ([Appendix 2](#)) will be applied as clinically applicable

